Heart rate (beat per min)†	X	X	X	X	X	X	X	X	X	
Respiratory rate (breath per min)†	X	X	X	X	X	X	X	X	X	
Arterial blood pressure (mmHg)†	X	X	X	X	X	X	X	X	X	
Clinical respiratory score†	X	X	X	X	X	X	X	X	X	
PCR	X									
Blood sample*	X									
VBG*	X			X						
Concomitant Medications	X	X	X	X	X	X	X	X	X	
Medical treatment‡	X	X	X	X	X	X	X	X	X	
Adverse event record	X	X	X	X	X	X	X	X	X	

If the patient was not discharged after 96 hours, the procedures mentioned above were continued.

†All parameters were measured during the resting of children.

*Samples were performed at any time if the clinician deemed it necessary.

Protocol No 1
Date: 10/03/2017
Revised 1: 10/03/2020
Revised 2:14/02/2021

**All children included in the study were phoned after 15 days post-discharge.

†The clinician decides to use medical treatments such as beta2 agonist, systemic steroid, and hypertonic saline.

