2.3 Secondary Objectives

- ✓ The mean difference in HR decreased compared with the baseline value from randomization to 96 hours (or to discharge)
- ✓ The mean difference in RR decreased compared with the baseline value from randomization to 96 hours (or to discharge)
- ✓ The mean difference in CRS regress compared with the baseline value from randomization to 96 hours (or to discharge)
- ✓ The length of hospital stays [from admission to discharge (hour)]
- ✓ The length of oxygen treatment [from admission to weaning to room air (hour)]

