5.3 Treatment Failure and Escalation of Care

- ✓ The clinician will decide on the escalation of care at any time if the Pediatric Early Warning Score (PEWS) is ≥ 7 points (Appendices 3).
- ✓ Treatment failure at 4 hours is considered when at least three of the following five criteria are present for both groups.
 1. No change or an increase in HR relative to baseline
 2. No change or an increase in RR relative to baseline
 3. Persistence of low SpO₂ ($<92\%$) in the three near independent measurements despite receiving FiO₂ $>40\%$ for HFNCOT and at a maximum 10 L/min for St-FMOT
 4. No change or an increase in CRS relative to baseline
 5. Blood pressure of carbon dioxide >60 mm/Hg
- ✓ Children with treatment failure at 4 hours or who need escalation of care will be treated as follows:
 - **Control Arm:** Children who deteriorate on the St-FMOT will receive HFNCOT (at 2 L*kg/min) as a rescue treatment in the ward or be transferred to the ICU for IMV.
 - **Experimental Arm:** Children who deteriorate on HFNCOT are admitted to the ICU for IMV as a rescue treatment.

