7.2 Data Analysis Methods

Categorical and continuous variables will be expressed as frequency (percentage) and median (IQR). Between groups, we will use the Mann-Whitney-U test for comparing the time of success for HR, RR, and CRS (SPSS Inc., version 25.0, Chicago, IL, USA). The longitudinal analysis part of the study will be performed non-parametrically with the Brunner Langer model for CRS conducted with a linear mixed model in a parametric way for HR and RR. Brunner Langer model (F1-LD-F1) is applied using web-based software (R software, version 3.5.2, package: nparLD, R Foundation for Statistical Computing, Vienna, Austria; <http://r-project.org>). The PROC MIXED procedure in the SAS software is used (Version 9.3; SAS Institute, Cary, NC, USA) to perform linear mixed models in which subjects will be included as random effects. When there is a significant interaction effect in the longitudinal analysis ($P < .1$), the time effect will be analyzed in each group, and groups will be compared at baseline and following time points (the baseline was subtracted from these time points). The proportions of the treatment failure at 4 hours, rescued patient, ICU admission, and AE are analyzed using Fisher's Exact test and given with odds ratio (OR) and 95% Confidence Interval (CI). We will perform intention-to-treat and per-protocol approaches for all outcomes. The time of success for HR, RR, and CRS outcomes will be analyzed using the PP approach. A 2-sided $P < .05$ defines statistical significance.

Statistical Analysis Plan

The biostatistician in the study, which has blinded to allocation, will perform the analysis. An interim analysis will not be performed. If substantial evidence of increased risk of harms ($p < 0.001$) observed in both groups, stopping rules will be used with the biostatistician's advice. Intention to treat and per-protocol approaches will be conducted if necessary.

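### No estimate or confidence interval is assured for the secondary change-from-baseline objectives (HR, RR, CRS): the visit comparisons are described only after an interaction P < .1

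*Combined protocol and SAP*

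**What the plan says.** Section 2.3 states the secondary objectives without any condition. For HR: "The mean difference in HR decreased compared with the baseline value from randomization to 96 hours (or to discharge". RR is worded the same way, and for CRS: "The mean difference in CRS regress compared with the baseline value from randomization to 96 hours (or to discharge".

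Section 7.2 fits a Brunner-Langer model to CRS, and for HR and RR "linear mixed models in which subjects will be included as random effects". The group comparison of changes is then introduced by a condition: "When there is a significant interaction effect in the longitudinal analysis", with the threshold set at P < .1. Once it is met, the time effect is examined within each group and "groups will be compared at baseline and following time points (the baseline was subtracted from these time points". The significance rule is general: "A 2-sided $P < .05$ defines statistical significance".

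The schedule of observations has eight post-baseline visits to 96 hours (1, 2, 4, 12, 24, 48, 72 and 96 h). Its note on longer stays reads: "If the patient was not discharged after 96 hours, the procedures mentioned above were continued". The only rule for truncated data, in section 3.4, censors at withdrawal and does not mention discharge.

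**The concern.** The objective is unconditional but its described analysis is conditional. Section 7.2 promises an odds ratio with a 95% CI for the binary safety outcomes. It promises no estimate or CI for the difference in HR, RR or CRS change when the interaction P is .1 or more.

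Three things are at stake. A modest effect may leave a stated objective without an estimate. Estimates that appear because an interaction test succeeded are too large on average. And when the condition is met, up to eight visits per outcome can each be declared significant at .05, with none named in advance as the one that counts.

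A fourth gap concerns discharge. The plan does not say whether the visit contrasts come from the mixed model, which uses all available visits, or from separate tests on children still in hospital. Recovered children leave first, so the two need not agree at late visits.

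**Working it through.** **The plan's own figure.** Section 7.1 raises 100 to 110 for 10% attrition: 100 × 1.10 = 110. Dividing instead gives 100/0.90 = 111.1, or 112 in two equal arms. The figure reproduces, and this point does not depend on it.

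**Effect sizes implied by section 7.1.** The pilot effects and SDs are not given. Solving a two-sided t-test at 80% power and alpha .05 for the standardised effect gives 0.566 SD for a total of 100 (CRS), 0.934 for 38 (RR) and 0.875 for 43 (HR). These totals were computed for the primary outcome, so for change scores they are only indicative.

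**Simulation inputs.** From the documents: 50 per arm (the stated minimum of 100), baseline plus eight visits, interaction threshold .1, visit tests on baseline-subtracted values at two-sided .05. Assumed: complete normal data for HR and RR; equal correlation of 0.3, 0.5 or 0.7, serial correlation by visit order of 0.5, 0.7 or 0.9, or intermediate patterns. The interaction was tested under both a random-intercept and an unstructured covariance, with 10,000–20,000 trials per setting.

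| True effect (HR, RR) | Interaction P < .1 | Mean 4 h estimate when met | Overstatement |
|---|---|---|---|
| 0.3 SD at all visits | 25–73% | 0.333–0.466 | 11–55% |
| 0.57 SD at all visits | 62–100% | 0.567–0.673 | 0–18% |
| 0.9 SD at all visits | 97–100% | 0.90–0.917 | 0–2% |
| 0.5 SD to 24 h, then none | 82–100% | 0.498–0.534 | 0–7% |

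The overstatement is the ratio to the truth, for example 0.333/0.30 = 1.11 and 0.466/0.30 = 1.55. If all visits correlate 0.9, the condition is met in about 95% of trials at 0.3 SD and the overstatement is about 2%.

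CRS was simulated separately with a Brunner-Langer interaction test on integer scores from 0 to 12. At 0.3 SD the condition is met in 20–48% of trials and the estimate is 21–60% too large. At 0.57 SD these are 59–97% and 1–20%.

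**False positives with no effect.** Eight independent tests would give 1 − 0.95^8 = 0.337. Visits share a baseline and are correlated, and the simulated rate without the interaction condition is 0.18–0.25. With the condition it is 0.055–0.10 per outcome for HR and RR, and 0.054–0.068 for CRS.

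**Against one unconditional contrast.** With 55 per arm, a constant 0.4 SD effect and equal correlation of 0.3, 0.5 or 0.7, the average change differs significantly in 65%, 79% or 95% of trials, with type I error of about 0.05. The interaction condition is met in only 45%, 59% or 82%.

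**Subtracting versus adjusting for baseline.** The variance ratio of adjusted to change score is (1 − r²)/(1 + k² − 2rk), where k is baseline SD over follow-up SD. At k = 1 and r = 0.3, 0.5 or 0.7 it is 0.91/1.4 = 0.65, 0.75/1 = 0.75 or 0.51/0.6 = 0.85. At k = 0.6 it is 0.91–0.99. At r = 0.5, k = 1 and 50 per arm, the 4 h CI half-width falls from 0.40 to 0.34 SD.

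**Discharge.** Assume that children leave after the 24, 48 or 72 h visit once below a recovery threshold, with 29–51% still present at 96 h. Under serial correlation, separate change-score tests at 48–96 h average 0.35–0.48 SD for a true 0.57. Under equal correlation there is no such loss (0.55–0.58). A baseline-adjusted unstructured mixed model averages 0.55–0.58 from 4 to 96 h.

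**The case against.** The strongest reply is that section 7.2 says when, not only when, and that the models are fitted regardless. With baseline as a time level, the group-by-time interaction is itself a test of differing change. This stands. A reader might infer that the section 2.3 objectives go untested unless P < .1, and the documents do not support that. What remains conditional is the visit-level comparison and any estimate or CI of the difference in change. A default overall group effect would not fill the gap, because it averages over baseline as well.

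A reader might also infer false-positive rates near one in three. The interaction condition removes most of that inflation.

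Nor can the plan be charged with a random-intercept-only model. Subjects as random effects may mean that, but no covariance structure is stated. The fair criticism is that it should be.

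On discharge, section 2.3 does bound the window, and a mixed model uses available data by default. The late loss arises only if the contrasts are separate tests and correlation is serial. The check of the mixed model is also favourable by construction: simulated discharge depended only on observed values, and the documents give no discharge criteria or timing.

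Finally, one might say that baseline adjustment affects precision alone. That holds under sound randomisation. Section 3.6 allocates by odd and even days in an open trial, so it cannot be assumed here.

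**Conclusion.** The concern holds in a limited form and should be fixed. Three unconditional secondary objectives have no assured estimate or CI, and when visit comparisons are made there is no pre-specified key contrast.

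The size depends on the true effect and on assumed correlations. At 0.3 SD the consequences are usually material. At about 0.9 SD, near the values implied for RR and HR, they are negligible. At 0.57 SD, the value implied for CRS, they range from nothing to a CRS estimate 20% too large and no visit-level estimate in about 41% of trials. Because the implied sizes belong to the primary time outcomes, they establish neither reassurance nor alarm for the change scores. The excess false-positive rate is modest.

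That late differences will be understated is a tempting inference but only a possibility, because the plan does not say which analysis produces the visit contrasts. The primary time-to-success comparisons are unaffected.

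**What to change.** **HR and RR.** Fit the post-baseline visits in PROC MIXED with group, visit, group-by-visit, baseline and baseline-by-visit. Report the baseline-adjusted group difference with 95% CI at each scheduled visit, whatever the interaction P. Take it from the model using all available visits, state that post-discharge visits are missing and assumed missing at random, and give the number observed per arm and visit.

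**One formal contrast per outcome.** Choose either the average post-baseline difference, which matches the section 2.3 window (state the visit weights), or one named visit. The 4 h visit is a candidate because section 5.3 already uses it: "Treatment failure at 4 hours is considered when at least three of the following five criteria are present for both groups". It can be expected to precede most discharges, although the documents give no discharge times. The other visits are descriptive.

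**Covariance.** State the structure and a fallback. Unstructured over eight visits means 8 × 9/2 = 36 parameters in about 110 children.

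**CRS.** Keep Brunner-Langer and add an unconditional baseline-adjusted difference with CI at an early visit before most discharges. Do not base late comparisons on adjusted analyses of children still in hospital unless a method that uses the discharged children's earlier scores is specified. With normal data as a proxy, such an adjusted comparison at 96 h averaged 0.29–0.43 SD for a true 0.57, against 0.37–0.59 for the change score.

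**Baseline.** A descriptive comparison may stay, given the odd/even-day allocation.

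**Cost.** SAP wording and model code only, since the data are already collected. The downsides are more parameters, wide late CIs (in the discharge check the standard error was 0.20–0.46 SD at 96 h against 0.14–0.20 at 4 h), and single later visits no longer formally tested.

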2.4 Safety Objectives

- ✓ The proportion of the treatment failure at 4 hours and escalation of care
- ✓ The proportion of the admission of ICU for IMV
- ✓ The proportion of adverse events

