6. SAFETY AND ADVERSE EVENT(S)

During the study, AEs, regardless of relatedness to the study device, will be reported on the AE page of the CRF (Appendices 4). All adverse reactions will be recorded in CRF and registered in the manuscript and clinicaltrial.gov. Open disclosure is paramount to the ongoing efficacy and ethical conduct of the trial, so parents/ legal guardians of participants experiencing AE are to be entirely briefed about the nature and effect of the AE. They are to be informed of likely consequences and alternative facts considered relevant following the standard disclosure duty.

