6.1 Definitions and Classification

✓ **Adverse Event (AE)**

Any untoward medical occurrence in a patient who is administered a pharmaceutical product or device does not necessarily have a causal relationship with this treatment. An AE is any unfavorable and unintended sign (including an abnormal laboratory finding), symptom, or disease temporally associated with the use of an investigational product.

✓ **Suspected Adverse Reaction**

Suspected adverse reaction means any adverse event for which there is a reasonable possibility that the drug caused the adverse event. For IND safety reporting purposes, 'reasonable possibility' means there is evidence to suggest a causal relationship between the drug and the adverse event. A suspected adverse reaction implies less certainty about causality than an adverse reaction, which means any adverse event caused by a drug.

✓ **Adverse Reaction**

An adverse reaction means any adverse event caused by a drug. Adverse reactions are a subset of all suspected adverse reactions where there is reason to conclude that the drug caused the event.

✓ **Unexpected Adverse Reaction**

An adverse event or suspected adverse reaction is considered as unexpected;

- ✓ Not listed in the investigator brochure or is not listed at the specificity or severity that has been observed
- ✓ An investigator brochure is not required or available
- ✓ Not consistent with the risk information described in the general research plan or elsewhere in the current application, as amended.
 - For example, under this definition, hepatic necrosis would be unexpected (under greater severity) if the investigator brochure referred only to elevated hepatic enzymes or hepatitis.

- Similarly, cerebral thromboembolism and cerebral vasculitis would be unexpected (under greater specificity) if the investigator brochure listed only cerebral vascular accidents.
- ✓ Unexpected as used in this definition, it also refers to adverse events or suspected adverse reactions mentioned in the investigator brochure as occurring with a class of drugs or as anticipated from the drug's pharmacological properties, but are not explicitly mentioned with the drug under investigation.

✓ Serious Adverse Reaction

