An adverse event or suspected adverse reaction is considered "serious" if, in the view of either the investigator or sponsor, it results in any of the following outcomes: Death, a life-threatening adverse event, inpatient hospitalization or prolongation of existing hospitalization, a persistent or significant incapacity or substantial disruption of the ability to conduct normal life functions, or a congenital anomaly/congenital disability. Important medical events that may not result in death be life-threatening, or require hospitalization may be considered serious when, based upon appropriate medical judgment, they may jeopardize the patient or subject and may require medical or surgical intervention to prevent one outcome listed in this definition. Examples of such medical events include allergic bronchospasm requiring intensive treatment in an emergency room or at home, blood dyscrasias or convulsions that do not result in inpatient hospitalization, or the development of drug dependency or drug abuse.

✓ Life-Threatening Adverse Reaction

An adverse event or suspected adverse reaction is considered "life-threatening" if, in the view of either the investigator or sponsor, its occurrence places the patient or subject at immediate risk of death. It does not include an adverse event or suspected adverse reaction that, had it occurred in a more severe form, might have caused death.

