Respiratory rate (breaths/minute)	0 to < 3 months	> 29 and < 61	≥ 61 or ≤ 29	≥ 81 or ≤ 19	≥ 91 or ≤ 15
	3 to < 12 months	> 24 and < 51	≥ 51 or ≤ 24	≥ 71 or ≤ 19	≥ 81 or ≤ 15
	1-4 years	> 19 and < 41	≥ 41 or ≤ 19	≥ 61 or ≤ 15	≥ 71 or ≤ 12
	>4-12 years	> 19 and < 31	≥ 31 or ≤ 19	≥ 41 or ≤ 14	≥ 51 or ≤ 10
	>12 years	> 11 and < 17	≥ 17 or ≤ 11	≥ 23 or ≤ 10	≥ 30 or ≤ 9
Respiratory effort		Normal	Mild increase	Moderate increase	Severe increase/any apnea
Oxygen saturation (%)		> 94	91 to 94	≤ 90	

Protocol No 1
Date: 10/03/2017
Revised 1: 10/03/2020
Revised 2:14/02/2021

Oxygen therapy		Room air		Any to < 4 L/minute or < 50%	≥ 4 L/minute or $\geq 50\%$
-----------------------	--	----------	--	------------------------------	----------------------------------

Appendices 4. Case report form

Case No and date								
Age (months)								
Gender	 Male		 Female					
Gestational age								
Body weight (gr/kg)								
Virus detected in RT-PCR	 Yes		 No					
If yes, which virus was detected								
Number of bronchiolitis	 1		 2		 3+			
Season	 Winter		 Autumn		 Spring		 Summer	
Study device	 St-FMOT  HFNCOT							
VARIABLES	Body temperature (°C)	Heart rate (bpm)	Respiratory rate (/min)	Arterial tension (mm/Hg)	SpO ₂ (%)	Venous blood gases	Ph-PCO ₂	CRS
At first admission								
1 h								
2 h								
4 h								
12 h								
24 h								

2 d							
3 d							
4 d							
5 d							
6 d							
7 d							
8 d							
9 d							
10 d							
Length of oxygen requirement (h)							
Length of hospital stay (d)							
Beta2 mimetic use?	 Yes		 No				
If yes, how many days did it use? (d)							
Inhaler corticosteroid use?	 Yes		 No				
If yes, how many days did it use? (d)							
IV corticosteroid use?	 Yes		 No				
If yes, how many days did it use? (d)							
Inhaler hypertonic saline use?	 Yes		 No				
If yes, how many days did it use? (d)							
Did any complications occur?	 Yes		 No				

Which complications occurred?			

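### Adverse events are compared only as one any-AE proportion that does not exclude worsening bronchiolitis, and serious events are neither recorded as a class nor analysed

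*Combined protocol and SAP*

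**What the plan says.** - **Objective.** Section 2.4 lists "The proportion of adverse events" as a safety objective, next to treatment failure or escalation and ICU admission for IMV. It makes no split by seriousness, relatedness or type.
- **Analysis.** Section 7.2: "The proportions of the treatment failure at 4 hours, rescued patient, ICU admission, and AE are analyzed" by Fisher's exact test, with odds ratios and 95% confidence intervals. AE is one of four binary safety outcomes; the other three concern failure of treatment or worsening of the illness.
- **Definition.** Section 6.1: "An AE is any unfavorable and unintended sign (including an abnormal laboratory finding), symptom, or disease temporally associated with the use" of the product. Section 6 adds that AEs are reported whether or not they relate to the device. Worsening bronchiolitis is neither named nor excluded.
- **Seriousness.** Section 6.1 defines serious by outcomes that begin "Death, a life-threatening adverse event, inpatient hospitalization or prolongation of existing hospitalization". It also defines life-threatening events and adverse reactions. No objective or analysis uses any of these classes.
- **Recording.** Section 6 says AEs "will be reported on the AE page of the CRF (Appendices 4"). The form printed in Appendix 4 has no such page. It asks "Did any complications occur" as a yes/no item, has a line for which complications, and has yes/no items for ICU transfer and failure at the fourth hour. The Schedule of Observations and Procedures requires an AE record at screening and at every time point to 96 h, but the time-point grid in Appendix 4 has no AE column.

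**The concern.** The AE numerator is not fixed. Under the literal 6.1 definition, a child whose bronchiolitis worsens has an AE as well as, possibly, a failure, a rescue or an ICU admission. A high carbon dioxide value, for example, is one of the section 5.3 failure criteria and could also be an abnormal laboratory finding. Under the Appendix 4 form, the numerator is instead whatever open-label staff regard as a complication.

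On the first reading, illness events common to both arms pull the AE odds ratio toward 1, and the AE result is not separate evidence from the failure, rescue and ICU results. On either reading, a minor skin mark and a pneumothorax count the same, and seriousness is not on the form. Because the schedule starts AE recording at screening and the form holds no onset, events present before treatment cannot be told from those that arise on it. A report of no difference in adverse events would then say little about the safety of the device.

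**Working it through.** **The plan's own figure.** The documents give no AE rate, AE effect or AE power. The sample size comes from efficacy outcomes: 100 × 1.10 = 110, or 55 per arm (dividing by 0.9 gives 112, a difference of two children).

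**Inputs.** From the documents: 55 per arm, Fisher's exact test, two-sided 0.05. Assumed: a shared background risk b of an illness event recorded as an AE, and an extra harm h in one arm only, independent of the background.

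**Formula.** Any-AE risk is b in one arm and 1 − (1 − b)(1 − h) in the other. Power is the sum of binomial probabilities over all pairs of counts with Fisher p < 0.05.

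For h = 12%:
- b = 10%: 1 − 0.90 × 0.88 = 20.8%
- b = 20%: 1 − 0.80 × 0.88 = 29.6%
- b = 40%: 1 − 0.60 × 0.88 = 47.2%; odds ratio (0.472/0.528)/(0.40/0.60) = 1.34

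| Extra harm h | Alone (b = 0) | b = 10% | b = 20% | b = 40% |
|---|---|---|---|---|
| 8% | 28% | 12% | 8% | 5% |
| 10% | 48% | 18% | 12% | 6% |
| 12% | 66% | 25% | 16% | 8% |
| 15% | 85% | 37% | 23% | 11% |

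**If HFNCOT also reduces worsening.** Assume device harm of 2% vs 20% and worsening of 30% vs 15% (St-FMOT vs HFNCOT). The any-AE risks are 1 − 0.98 × 0.70 = 31.4% and 1 − 0.80 × 0.85 = 32.0%. Power is 3%, against 83% for the harm tested alone. A benefit on the illness can mask a harm from the device.

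**Limits of any test at this size.** With no events in the other arm, Fisher gives p = 0.24 for 3 of 55, 0.12 for 4, 0.057 for 5 and 0.027 for 6. Power tested alone is 11% for a 6% harm and 2% for a 4% harm. An interval is more informative: 0 of 55 has an exact upper 95% limit of 1 − 0.025^(1/55) = 6.5%.

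**The case against.** The strongest objection is that the overlap is inferred. Section 6.1 is a generic definition, worsening has its own named outcomes, and Appendix 4 records failure, ICU transfer and complications as separate items, which may point to separate counting. With no shared background there is no dilution. This stands: a reader might infer that worsening will be counted and that harm is therefore diluted, but the documents support only that it can be.

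A reader might also infer that serious harms go unrecorded. That is too strong. ICU transfer is recorded and tested, the free-text line could name a pneumothorax, section 4.2 records device-related events at the day-15 call, and section 6 has all adverse reactions recorded and published. What is missing is the serious class itself, an onset field and any planned comparison. The Appendix 2 questionnaire is not reproduced in the text available, so the content of the day-15 call cannot be judged.

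A third tempting reading is that pooling is what would hide a few serious device harms. The figures do not support it: 0 vs 5 of 55 is not significant even when tested alone. The 66% figure also assumes no such event in the other arm. This counts against adding another significance test. It does not justify leaving the class unrecorded.

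**Conclusion.** The point holds as a gap in definition, recording and reporting of a safety objective; it does not touch the primary result. One any-AE proportion is the only AE comparison, the serious class is not captured as a class or analysed, and the AE page cited in section 6 is not in Appendix 4. These three facts rest on the text alone.

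The loss of information is conditional. For an extra harm of 12%, power falls from 66% to between 25% and 8% as the shared background runs from 10% to 40%. This assumes that worsening is recorded as an AE, that harm and illness events are independent, and rates that the documents do not supply. If staff record only narrow complications, the dilution shrinks, but section 6.1 and the form then disagree about what an AE is. Either way the plan needs the clarification.

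**What to change.** 1. **Appendix 4.** Add the AE page that section 6 refers to: event, onset date and time, serious yes/no, device-related yes/no, worsening of bronchiolitis yes/no.
2. **Section 7.2.** Replace the single AE test with a report by arm, as counts with exact 95% confidence intervals, of:
   - children with at least one serious AE as defined in 6.1, shown with and without worsening of bronchiolitis, because prolonged hospitalization would otherwise bring worsening back in;
   - children with at least one AE that starts after treatment start, other than worsening of bronchiolitis, which stays under failure, rescue and ICU admission.
3. List device-related AEs by arm, and keep any-AE as a descriptive count.

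The cost is one CRF page and a few lines in 7.2, with no added significance test. The downside is that unblinded staff must judge what is worsening and what is device-related. Showing the any-AE count alongside, and the serious AEs both ways, lets a reader see how far the result depends on that judgement.

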- ✓ To evaluate the effect on HR, RR, and CRS
- 1. The time it takes for HR to reach its normal range for age (hour)
- 2. The time it takes for RR to reach its normal range for age (hour)
- 3. The time it takes for CRS to regress from severe [scores of 9-12] to moderate [scores of 5-8] bronchiolitis, or from moderate [scores of 5-8] to mild [scores of 0-4] bronchiolitis (hour)

B. Secondary Objectives

- ✓ The decrease in HR compared with the baseline value
- ✓ The decrease in RR compared with the baseline value
- ✓ The decrease in CRS compared with the baseline score
- ✓ The effect on LOS and LOOT

C. Safety Objectives

- 1. The proportion of treatment failure at 4 hours or escalation of care
- 2. The proportion of admission to ICU for IMV
- 3. The proportion of adverse event

Rationale

- ✓ There has been insufficient RCT conducted on children with moderate and severe bronchiolitis requiring oxygen therapy in the general ward.

Study Population

A. Inclusion Criteria

- ✓ Children aged between 1 and 24 months with moderate and severe bronchiolitis requiring oxygen supplement.

B. Exclusion Criteria

- ✓ Children with mild bronchiolitis
- ✓ Those with not requiring oxygen therapy
- ✓ Those admitted to ICU for urgent IMV
- ✓ Those who received supplemental oxygen or HFNCOT at other facilities before arrival

- ✓ Those with known comorbidity (such as congenital heart disease, chronic lung disease, neuromuscular disease, metabolic disease, and immunocompromised)
- ✓ Those with a craniofacial malformation, an upper airway obstruction, pneumothorax, or nasal trauma

Study Design

- ✓ Open-label, two-arm, phase 4 randomized controlled trial

Sample size (each group)

- ✓ 55 in each group (HFNCOT and St-FMOT)

Investigational treatment:

- ✓ Fisher & Paykel MR850 with Optiflow™ Junior Nasal Cannula System

Control Group

- ✓ St-FMOT

Duration of Treatment

- ✓ From admission to EUMF Pediatric Hospital to at 15 days of post-discharge

Centre/s

- ✓ Single-center – EUMF/Pediatric Hospital

Statistical Methods

- ✓ Chi-Squared Test, Fisher's Exact Test, Mann-Whitney-U Test, Linear Mixed Model, Bruner Langer Method

SCHEDULE OF OBSERVATIONS AND PROCEDURES

Diagnosis bronchiolitis	Screening ED or PPU	1h	2h	4h	12h	24h	48h	72h	96h	Phone follow-up
Inclusion/Exclusion criteria	X									X**
Informed consent	X									
Medical History	X									
Physical exam	X	X	X	X	X	X	X	X	X	
Bodyweight and length	X									
Body temperature (°C)	X	X	X	X	X	X	X	X	X	

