7. STATISTICAL METHODS

7.1 Sample Size

Sample size calculations were done using a t-test on the primary outcome. Based on our pilot trial to obtain a power of 80% and alpha of 0.05 with a 1:1 proportion of control to intervention groups, the sample size yielded a total of 100 participants for CRS, 38 for RR, and 43 for HR. Given these sample sizes, we chose to recruit a minimum of 100 subjects. However, the final sample size was 110 patients, considering the study's longitudinal aspect (with a 10% attrition rate).

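### Safety proportions are contrasted only by an odds ratio, which has no finite value when an arm of 55 has no events; a risk difference with a 95% CI should be added

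*Combined protocol and SAP*

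**What the plan says.** Section 2.4 states all three safety objectives as proportions, for example "The proportion of the admission of ICU for IMV". For 4-hour failure, rescue, ICU admission and adverse events, section 7.2 names one test and one contrast: "Exact test and given with odds ratio (OR) and 95% Confidence Interval (CI", the test being Fisher's. It names no method for the odds ratio interval, no rule for an arm without events, and no risk difference. The same section plans descriptive reporting: "Categorical and continuous variables will be expressed as frequency (percentage) and median (IQR". Counts and percentages per arm are therefore covered. The synopsis gives the size as "55 in each group (HFNCOT and St-FMOT". Section 7.1 derives that size from the clinical respiratory score (CRS), respiratory rate and heart rate, not from any safety event, and no expected safety event rate appears anywhere in the document.

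**The concern.** An odds ratio needs events in both arms to take a finite, non-zero value. For an uncommon outcome, such as ICU admission for invasive ventilation may be, 55 per arm may not supply them. The between-arm result would then reduce to a non-significant P beside a ratio of 0, infinity or nothing. A reader could take that as reassurance, when the data would still allow an excess of several percentage points. The objective is on the proportion scale, so the natural contrast, a difference in proportions, is the one that is missing. A second, smaller issue is that the interval method is left open: a large-sample (Wald) interval and Fisher's P are different procedures and can point in different directions on the same table.

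**Working it through.** **Inputs.** 55 per arm (synopsis); Fisher's test, odds ratio and 95% CI (section 7.2); two-sided 5% level (section 7.2). Event rates are assumptions, because the document gives none.

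**The plan's own size.** Section 7.1 reports that "the sample size yielded a total of 100 participants for CRS, 38 for RR, and 43 for HR", then that "the final sample size was 110 patients, considering the study's longitudinal aspect (with a 10% attrition rate". 100 × 1.10 = 110, or 55 per arm. Dividing instead by 0.90 gives 111.1, or 112 as an even total, so 110 is reproduced closely enough. The base figures cannot be re-derived, because the pilot means and SDs are not given.

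**Chance of an empty arm.** With true rate p in both arms, one arm is empty with probability q = (1 − p)^55, and at least one arm with 1 − (1 − q)².

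| Assumed p | q | At least one arm empty | Both arms empty (q²) |
|---|---|---|---|
| 1% | 0.575 | 82% | 33% |
| 2% | 0.329 | 55% | 11% |
| 3% | 0.187 | 34% | 3.5% |
| 5% | 0.060 | 12% | 0.4% |
| 10% | 0.003 | 0.6% | about 0% |

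**What the odds ratio gives with an empty arm.** The Wald interval cannot be computed. The exact conditional interval keeps one finite bound:

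- 3 v 0: P = .243, OR infinite, CI 0.42 to infinity.
- 5 v 0: P = .057, OR infinite, CI 0.95 to infinity.
- 6 v 0: P = .027, OR infinite, CI 1.24 to infinity.
- 0 v 0: OR undefined, CI 0 to infinity.

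**What the data still allow.** The two-sided 95% Clopper-Pearson upper limit for 0/55 is 1 − 0.025^(1/55) = 6.5%.

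**What a risk difference gives.** Newcombe 95% intervals, in percentage points:

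- 0 v 0: 0 (−6.5 to 6.5).
- 1 v 0: 1.8 (−4.9 to 9.6).
- 3 v 0: 5.5 (−2.0 to 14.9).
- 5 v 0: 9.1 (0.8 to 19.6).

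All are finite. At 5 v 0 the interval excludes 0 while Fisher's P is .057.

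**P against the odds ratio interval.** For 12 v 4, OR = (12 × 51)/(43 × 4) = 3.56. The standard error of the log OR is √(1/12 + 1/43 + 1/4 + 1/51) = 0.613, so the Wald interval is exp(1.269 ± 1.96 × 0.613) = 1.07 to 11.84, beside Fisher P = .056. Over all 54 × 54 = 2,916 tables with no zero cell at 55:55, the two disagree in 78 (39 if mirror images are merged), always with P at or above .05 and an interval excluding 1. The conflict with the fewest events is 9 v 2. The combined probability of these tables is 0.06, 0.8 and 1.9% when both true rates are 5, 10 and 30%, and about 7% at 10% v 30%.

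The exact conditional interval for 12 v 4 is 0.97 to 16.07, which agrees with P. That method disagreed with Fisher in 0 of 96 near-threshold tables at 55:55. With unequal arms it can disagree: at an illustrative 58:52, in 10 of 97, for example 0/58 v 4/52, P = .047 with CI 0 to 1.32.

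**The case against.** Fisher's test with an odds ratio is a standard choice for small counts, and its conservatism is a known property rather than an error. Per-arm counts and percentages are planned, so a reader could work out a risk difference. The event rates above are assumed, and for some outcomes low rates are doubtful. Section 6 records adverse events whether or not related to the device, and section 6.1 defines them broadly, so that proportion may well not be 1 or 2%. Section 5.3 sends children who deteriorate on high flow to the ICU, so ICU admission in that arm need not be rare. Equally, section 5.3 allows control children ward rescue with high flow, so the control arm could have few ICU admissions. The documents settle neither point.

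Most of this stands, and it limits the point to a minor one. It does not remove it: percentages without an interval do not show how large an excess remains compatible with the data, and leaving each reader to derive the contrast is not a plan.

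A reader might also infer that P and interval will clash for the rarest harms. The documents do not support that. No interval method is named, the clash needs a Wald interval or unequal arms, and with a Wald interval at 55:55 it does not arise below 9 v 2.

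**Conclusion.** The point holds as a cheap improvement of minor severity. For safety outcomes with true rates of about 3% or less, the planned contrast has a substantial chance (34 to 82% at assumed rates of 3 to 1%) of yielding no finite estimate. At 5% the chance is 12%, and at 10% it is negligible. These figures assume the same rate in both arms and exactly 55 per arm. Day-based allocation (section 3.6) and per-protocol sets (section 7.2) make equal arms uncertain.

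Three stronger readings are not supported. The odds ratio is not undefined whenever an arm is empty: with one empty arm it is 0 or infinite, an exact interval keeps one bound, and only 0 v 0 is undefined. The rarest harms are not left without any usable figure, because counts and percentages are planned. And nothing in the plan requires Fisher's test to be replaced or a safety conclusion to rest on an upper confidence limit: safety is not a primary objective, and no safety margin or equivalence claim is stated.

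**What to change.** In section 7.2, keep Fisher's test and the odds ratio. For each of 4-hour treatment failure, rescue, ICU admission and adverse events, add the risk difference with a 95% CI that stays defined at zero events, such as a Newcombe or exact unconditional score interval, and name the method before the counts are seen. Where an odds ratio is shown, use the exact conditional interval, and state that at 0 v 0 the odds ratio is reported as not estimable.

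The cost is a few lines of SAP wording, a procedure option and one more reported figure; no extra data or patients are needed. The drawback is that the risk difference interval will occasionally differ from Fisher's P, as at 5 v 0. The SAP should therefore say that the interval is for estimation and that the test remains Fisher's.
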